9.2 STATISTICAL ANALYSES

9.2.1 GENERAL APPROACH

All statistical tests will be 2-sided. The outcome measures will be tested at a 0.05 level of significance. SPSS will be used to conduct the statistical analyses. All participants who have EAW sessions will be included (regardless of the number of sessions they complete before discharge, but the number and reason of missing EAW sessions will be recorded). To test the three main hypotheses of the proposed study, the change score of each outcome between baseline and discharge will be calculated. The change score will be compared between the intervention and control groups using independent t-test analyses (if the outcomes are not normally distributed, Mann-Whitney tests will be used).

In addition to the primary analysis, several secondary analyses will be performed. 1) Each of the outcomes will be compared between pre- and post-EAW training using a paired t-test analysis (if the outcomes are not normally distributed, Wilcoxon signed-rank test will be used). 2) Analyses will be performed to determine the relationships between the change of outcome measures and EAW training time (including sessions, up time, walking time, or total number of steps per session and across all sessions) using correlation coefficients, regression analyses (stepwise and logistic), analyses of covariance, and nonparametric analyses as appropriate. 3) An additional exploratory post

hoc analyses will be to determine the relationship of participant's baseline characteristics with successful use of the exoskeleton. This post hoc analysis would serve as pilot data to begin to determine who is a good candidate for EAW training during AIR for a future study.

References:

1. Simpson, L.A., et al., *The health and life priorities of individuals with spinal cord injury: a systematic review*. J Neurotrauma, 2012. **29**(8): p. 1548-55.
2. Ditunno, P.L., et al., *Who wants to walk? Preferences for recovery after SCI: a longitudinal and cross-sectional study*. Spinal Cord, 2008. **46**(7): p. 500-6.
3. Tate, D.G., C.Z. Kalpakjian, and M.B. Forchheimer, *Quality of life issues in individuals with spinal cord injury*. Arch Phys Med Rehabil, 2002. **83**(12 Suppl 2): p. S18-25.
4. [name], T.N. and K.T. Ragnarsson, *Pain after spinal cord injury*. Phys Med Rehabil Clin N Am, 2000. **11**(1): p. 157-68.

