5 STUDY POPULATION

5.1 INCLUSION CRITERIA

1. Age 18 years or greater
2. Height between 5'2" and 6'2" (1.6 meters to 1.9 meters)
3. Weight less than 220 pounds (100 kilograms)
4. Near Normal range of motion (ROM), as follows: 1) Hip: more than 5 degrees of extension and 110 degrees of flexion; 2) Knee: Full extension to 110 degrees of flexion; 3) Ankle: at least 0 degree of dorsiflexion to 25 degrees of plantarflexion
5. Are eligible for locomotor training as part of inpatient rehabilitation
6. Independent with static sitting balance
7. Sufficient function upper extremity strength to manage walking aid (front-wheeled walker, platform walker, or crutches)
8. Able to follow directions

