5.2 EXCLUSION CRITERIA

1. Uncontrolled cardiovascular conditions (i.e. heart failure, angina, hypertension)
2. Inability to sit upright due to orthostatic hypotension
3. Any form of progressive SCI as defined by the physician, such as cancers
4. Upper leg length discrepancy > 0.5" or lower leg discrepancy >0.75"
5. Skin integrity issues in areas that would contact the device or that would likely be made worse by device use
6. Pregnancy, colostomy, mechanical ventilation
7. Any other medical issue in the judgment of his/her clinicians that might prevent safe standing or walking
8. Non-English Speaking
9. Cognitive and/or communicative disability (e.g. due to brain injury). Participants must be able to follow directions well and demonstrate learning capability.

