6 STUDY INTERVENTION

6.1 STUDY INTERVENTION(S) ADMINISTRATION

6.1.1 STUDY INTERVENTION DESCRIPTION

Intervention (N=20): In the intervention group, participants will receive locomotor training provided with an Ekso™ powered exoskeleton according to the standard of care of AIR at Mount Sinai Hospital with the exception that the EAW training will be incorporated into the designated therapy times (3 hours of physical therapy (PT) and/or occupational therapy (OT)) which will be provided as determined by the clinical team from the earliest time they are identified to be able to safely stand, through discharge. The goal of EAW intervention is to complete three or more sessions of EAW training a week during the AIR period (after enrolling into the study until discharge). One EAW session is defined to have at least 20 minutes of uptime in the device (based on data output from EksoTM, device, not including donning and doffing time). EAW sessions will include device fitting, instruction for sit-to-stand and stand-to-sit maneuvers; balance and fall protection training; and walking on smooth indoor surfaces with total or variable device assistance. The clinical team will determine the frequency, duration, and intensity of each EAW session based on the participant's response to the previous session.

Control (N=10): In the control group, participants will receive standard of care AIR which includes three hours of PT and/or OT per day until they are discharged. This standard of care AIR may include bed mobility, balance, strength, gait, transfers, and wheelchair mobility training to improve participants' independence in activities of daily living, such as bathing, eating, dressing, grooming, and wheelchair use but does not include EAW. The two groups (control and intervention) will have the same total amount of therapy time.

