6.2 MEASURES TO MINIMIZE BIAS: RANDOMIZATION AND BLINDING

Eligible participants will be randomized into either the intervention group or the control group. In order to provide more opportunities for participants to accept EAW training, the intervention group will have 20 participants, and the control group will have 10 participants.

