9 STATISTICAL CONSIDERATIONS

9.1 SAMPLE SIZE DETERMINATION

All statistical tests will be 2-sided. The outcome measures will be tested at a 0.05 level of significance. SPSS will be used to conduct the statistical analyses. All participants who have EAW sessions will be included (regardless of the number of sessions they complete before discharge, but the number and reason of missing EAW sessions will be recorded). To test the three main hypotheses of the proposed study, the change score of each outcome between baseline and discharge will be calculated. The change score will be compared between the intervention and control groups using independent t-test analyses (if the outcomes are not normally distributed, Mann-Whitney tests will be used).

Since the primary aim of the study is to compare the improvement of FIM scores between the groups, the FIM score results from the preliminary data were used to perform the power analysis for this study. In the preliminary data, the mean change in FIM score from the intervention group was 35 ± 12 , and the control group was 22 ± 13 . The effect size of the FIM score change in our preliminary data was 1.07 (controlling for the different number of participants between the two groups). The power analysis showed that using the effect size (1.07) and 0.05 level of significance with two-sided analysis in independent t-test, a total of 30 participants will provide the study 80% power.

To account for an expected attrition rate of about 25%, 40 participants will be enrolled. It is expected that 30 participants will complete the study (the reasons and number of screening failures and dropouts will be recorded).

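### The only inclusion rule for the analysis is having EAW sessions; no as-randomised set is defined, so EAW-arm participants with no session could be left out while all controls stay in

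*Combined protocol and SAP*

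**What the plan says.** Sections 9.1 and 9.2.1 carry the same inclusion sentence: "All participants who have EAW sessions will be included (regardless of the number of sessions they complete before discharge". It goes on to say that the number of missed sessions, and the reasons, will be recorded. The primary comparison follows: "The change score will be compared between the intervention and control groups using independent t-test analyses".

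Four other parts of the document bear on it:

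- Section 6.2 forms the two groups by randomisation: "Eligible participants will be randomized into either the intervention group or the control group". The planned sizes are 20 and 10.
- Section 6.1.1 describes control care as standard rehabilitation that includes gait and other training "but does not include EAW".
- Section 6.1.1 also says that EAW is given "from the earliest time they are identified to be able to safely stand, through discharge", and it defines a session as at least 20 minutes of uptime in the device.
- Section 7.1 allows a participant to be withdrawn over concerns that arise during an exoskeleton instruction session.

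No section defines an intention-to-treat, as-randomised or per-protocol set. No section says how a participant randomised to EAW who has no session is to be handled.

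**The concern.** The sentence sets a condition that only one arm can meet. Taken literally for everyone it would remove all controls, which cannot be intended because the next sentences compare the two groups. The reader must therefore supply the rule, and two are available: an adherence clause inside a comparison of randomised groups, or a filter on the EAW arm alone.

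The parenthesis keeps people who had few sessions. It qualifies participants who have sessions, so it does not clearly reach those who have none. If the definition in section 6.1.1 governs, a participant who tried the device but never reached 20 minutes of uptime may also count as having none.

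Having a first session happens after randomisation and depends on the clinical team judging that the participant can stand safely. If non-starters differ in prognosis and are removed from one arm only, the comparison loses the protection of randomisation. The direction could go either way: towards EAW if poor recoverers do not start, away from EAW if fast recoverers are discharged first, and nil if not starting is unrelated to prognosis. The withdrawal route in section 7.1 adds a second way in which one arm alone can lose participants.

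**Working it through.** **Inputs from section 9.1.** FIM change 35 ± 12 (EAW) and 22 ± 13 (control), a difference of 35 − 22 = 13 points; effect size d = 1.07; two-sided α = 0.05; total 30; about 25% attrition. Group sizes of 20 and 10 are from section 6.2.

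**Assumed inputs.** The number k of the 20 EAW participants with no session, the correlation r between prognosis and FIM change (0.3 to 0.7), and the way non-starters are selected. The documents give none of these.

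**The plan's own power figure.** The noncentrality is d / √(1/n₁ + 1/n₂).

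- 15/15: 1.07 / √(2/15) = 2.93 on 28 df, power 80.7%. This reproduces the stated 80%.
- 20/10: 1.07 / √(1/20 + 1/10) = 2.76 on 28 df, power 76.0%.

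The gap between these two is a separate matter. The 76.0% serves here only as the baseline with nobody unexposed.

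**Bias if non-starters are dropped from one arm, with no true effect.** If the k participants with the lowest prognosis of 20 are removed, the mean prognosis of the rest rises by minus the sum of the k lowest expected normal scores, divided by 20 − k. Bias = r × 13 × that rise. The two lowest expected scores of 20 are −1.867 and −1.408.

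- k = 1: rise 1.867/19 = 0.098 SD. Bias 0.38, 0.64, 0.89 points at r = 0.3, 0.5, 0.7.
- k = 2: rise (1.867 + 1.408)/18 = 0.182 SD. Bias 0.71, 1.18, 1.66 points.

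Simulation (200,000 null trials per case, pooled t-test) agrees on the bias and gives the type I error:

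| Selection of non-starters | Lost of 20 | Bias (FIM points) | Type I error |
|---|---|---|---|
| Exactly the lowest prognosis | 1 | 0.4 to 0.9 | about 5 to 6% |
| Exactly the lowest prognosis | 2 | 0.7 to 1.7 | 5.3 to 7.2% |
| Graded (odds of not starting ×2 or ×4 per SD worse) | mean 1 | 0.1 to 0.6 | 5.1 to 5.3% |
| Graded, same odds | mean 2 | 0.3 to 1.1 | 5.0 to 5.6% |

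At r = 0 there is no bias. If the best-prognosis participants are removed instead (r = 0.5), the bias is about −0.6 (k = 1) or −1.2 (k = 2).

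**Price of the as-randomised analysis.** Suppose the k unexposed participants change as controls do. The average effect shrinks to d × (1 − k/20), for example 1.07 × 0.95 = 1.02 for k = 1. That gives the upper power figure below. The lower figure simulates the mixture itself, which also widens the spread within the EAW arm.

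| k unexposed | As randomised (20/10) | Excluded, d kept at 1.07 |
|---|---|---|
| 1 | 70.4 to 71.7% | 75.2% (19/10) |
| 2 | 64.4 to 67.0% | 74.3% (18/10) |
| 4 | 52.0 to 56.9% | 72.1% (16/10) |

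**The case against.** The strongest reply is that the sentence is about adherence. Its second half is about logging missed sessions, it makes no sense as a filter on both arms, and the test that follows compares the groups that section 6.2 forms by randomisation. Nowhere does the plan say that zero-session participants are dropped. This stands as a plausible reading, perhaps the more natural one. It does not settle the matter, because no other sentence defines the analysis set.

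The affected group may also be empty. Entry criteria include "Are eligible for locomotor training as part of inpatient rehabilitation", independent sitting balance and enough arm strength to manage a walking aid. Exclusions include "Any other medical issue in the judgment of his/her clinicians that might prevent safe standing or walking". This too stands: the number should be small. Eligibility does not guarantee a session, however, since the start of EAW is a separate, later judgement.

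Third, the sizes above are assumption throughout, and most of the type I errors are hard to tell from 5%. That is accepted, and it limits the weight of the point.

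A reader might infer something stronger: that the plan prescribes a per-protocol analysis that favours EAW, or that the false-positive rate is materially inflated. The documents support neither. Reaching 8 to 9% takes 20 to 25% non-starters who recover a full SD less, and nothing in the plan points to such figures.

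**Conclusion.** The point holds as a low-impact defect that should be fixed. The only stated inclusion rule rests on an event after randomisation that only the EAW arm can have, and no as-randomised set stands beside it. Whether anyone would be excluded, how many, and in which direction the result would move cannot be determined from the documents.

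Under the assumptions shown, the bias from losing 1 or 2 of 20 poor-prognosis participants is at most about 13% of the preliminary difference (1.7/13), and it could be nil or reversed. The stronger argument for acting is the choice left open: with 2 unexposed participants, power is 64 to 67% or about 74% depending on which set is used, and the plan does not fix which.

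Defining the set does not settle everything. An as-randomised analysis still needs a discharge score, and section 9.1 expects losses: "To account for an expected attrition rate of about 25%, 40 participants will be enrolled". Some of these may be screening failures before randomisation, so that 25% should not be read as the rate of missing discharge scores.

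**What to change.** In sections 9.1 and 9.2.1, replace the inclusion sentence with: *The primary analysis compares participants in the group to which they were randomised, regardless of whether or how many EAW sessions they received, and includes every randomised participant with a baseline and discharge score.*

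Make section 7.1 consistent by separating stopping EAW from leaving data collection. The discharge assessments already planned are then still sought from participants who never start or who stop EAW, unless they withdraw consent. The clinical grounds for stopping are not touched.

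Report by arm the numbers randomised, with no EAW session, withdrawn, and with missing discharge scores. Keep the EAW-exposed set for supplementary and dose-response analyses, labelled as such.

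The cost is wording in three sections, some effort to obtain assessments from people who have stopped EAW, and dilution: about 3 to 5 percentage points of power with 1 unexposed participant and 7 to 10 with 2, compared with excluding them. Possible bias from missing discharge scores remains, and the counts by arm only make it visible.

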1 PROTOCOL SUMMARY

1.1 SYNOPSIS

Title:	The Effects of Incorporated Exoskeletal-Assisted Walking in SCI Acute Inpatient Rehabilitation
Study Description:	A randomized controlled trial
Objectives:	
Primary Objective: Primary Objectives: To determine the effects of acute inpatient rehabilitation (AIR) with exoskeletal-assisted walking (EAW) compared with AIR without EAW (same total therapy time) on the changes from admission to discharge in the International Standards for Neurological Classification of Spinal Cord Injury (ISNCSCI) upper and lower extremity motor scores, Functional Independence Measure (FIM) scores, and Spinal Cord Independence Measure (SCIM) scores as classified by clinicians. Primary hypothesis: At discharge, compared to the baseline data (collected at admission), the AIR with EAW group will have significantly greater changes in ISNCSCI, FIM, and SCIM scores compared to the AIR without EAW group.
 
Secondary Objectives: To determine the effects of AIR with EAW compared to AIR without EAW on reducing pain using the International Spinal Cord Injury Basic Pain Data Set 2.0 (ISCIBPDS 2.0) measures where type of pain is classified with the Spinal Cord Injury Pain Instrument (SCIPI). Secondary hypothesis: At discharge, compared with baseline, the AIR with EAW group will report significantly more reduction in the average intensity of the participant's worst pain over the preceding 7 days than the AIR without EAW group.
 
Tertiary Objectives: To determine the effects of AIR with EAW compared with AIR without EAW on reducing a specific systemic inflammatory mediator (C reactive protein, CRP). Tertiary hypothesis: At discharge, as compared with baseline, the AIR with EAW group will have greater reductions in measured values for CRP than the AIR without EAW group.

Endpoints:	
Primary Endpoint: The changes from admission to discharge in the International Standards for Neurological Classification of Spinal Cord Injury (ISNCSCI)

upper and lower extremity motor scores, Functional Independence Measure (FIM) scores, and Spinal Cord Independence Measure (SCIM) scores

Secondary Endpoints: Pain evaluation using the International Spinal Cord Injury Basic Pain Data Set 2.0 (ISCIBPDS 2.0) measures where the type of pain is classified with the Spinal Cord Injury Pain Instrument (SCIPI).

Tertiary Endpoints: systemic inflammatory mediator (C reactive protein, CRP)

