Powered exoskeletons are a technology that can offer overground locomotion for people with SCI who would ordinarily be unable to walk and have been suggested as a way to promote increased function and quality of life [39]. In studies pioneered by [name] (co-mentor), exoskeletons have been studied in the chronic (>6 months post) SCI population for about seven years with preliminary reports showing benefits in mobility, health and quality of life (QOL) outcomes [40, 41]. While walking in an exoskeleton, people with SCI stand upright with full weight bearing through the feet [41] and walk while activating trunk and lower limb muscles. This activation may facilitate improvements in neuroconnectivity [39]. EAW has several benefits over BWSTT. It provides ground gait training experience that offers the potential benefits of standing and gait training with just one trainer and requires less of a constant equipment space allotment in an inpatient rehabilitation setting. EAW also possesses the unique potential for use after inpatient discharge to continue training and allow functional use in home, work, and community settings.

Previous studies show that EAW can elicit moderate-intensity activity for people with SCI, and participants can learn to walk without hands-on physical assistance by another person [40, 42-44]. Subjective reports from inpatients who were given the opportunity to use an exoskeleton during AIR in Mount Sinai Hospital had comments such as: "it was really great to have the legs moving again", "walking helped with regaining trunk support" and resulted in "good sensations in the legs and feet".

Despite the potential functional and health benefits of using EAW training in persons in SCI AIR, there are few studies published that have used, or are using an EAW intervention in early inpatient rehabilitation for patients with acute/sub-acute SCI. As such, there is a critical gap in knowledge that limits the use of EAW across the clinical care spectrum in SCI: we don't know if the EAW can be

effectively incorporated in clinical practice and if adding EAW into AIR program is better than traditional AIR without EAW. We expect this prospective randomized control trial (RCT) to determine if EAW training during AIR is a feasible, safe and efficacious approach to facilitate functional independence and to reduce post-SCI pain, as well as inflammation.

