3 OBJECTIVES AND ENDPOINTS

OBJECTIVES	ENDPOINTS
Primary	
To determine the effects of AIR with EAW compared with AIR without EAW (same total therapy time) on the changes from admission to discharge in the International Standards for Neurological Classification of Spinal Cord Injury (ISNCSCI) upper and lower extremity motor scores, Functional Independence Measure (FIM) scores, and Spinal Cord Independence Measure (SCIM) scores as classified by clinicians.	ISNCSCI examination results FIM scores SCIM scores
Secondary	
To determine the effects of AIR with EAW compared to AIR without EAW on reducing pain using the International Spinal Cord Injury Basic Pain Data Set 2.0 (ISCIBPDS 2.0) measures where type of pain is classified with the Spinal Cord Injury Pain Instrument (SCIPI).	Intensity of pain
Tertiary/Exploratory	
To determine the effects of AIR with EAW compared with AIR without EAW on reducing a specific systemic inflammatory mediator (C reactive protein, CRP).	CRP results

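### Section 9 tests the functional, pain and CRP hypotheses on an equal footing at two-sided 0.05 and does not carry over the primary/secondary/exploratory ranking of Sections 1.1 and 3

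*Combined protocol and SAP*

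**What the plan says.** Section 1.1 states three labelled hypotheses. The primary is that the exoskeleton group "will have significantly greater changes in ISNCSCI, FIM, and SCIM scores compared to the AIR without EAW group". The secondary is that "the AIR with EAW group will report significantly more reduction in the average intensity of the participant's worst pain over the preceding 7 days", again relative to control. The tertiary concerns CRP. Section 3 repeats the ranking and files CRP under "Tertiary/Exploratory".

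The analysis text, given in the same words in Sections 9.1 and 9.2.1, reads: "To test the three main hypotheses of the proposed study, the change score of each outcome between baseline and discharge will be calculated". It adds: "All statistical tests will be 2-sided"; "The outcome measures will be tested at a 0.05 level of significance"; and "The change score will be compared between the intervention and control groups using independent t-test analyses", with a Mann-Whitney test if the data are not normal.

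Section 9.2.1 uses the word secondary for within-person pre/post tests and training-dose relationships, and the word exploratory for an analysis of who is a good candidate. The between-group pain and CRP comparisons are in neither group. Section 9.1 calls the comparison of FIM improvement the primary aim and bases the power calculation on FIM alone. Neither section gives a testing order, a split of alpha or a multiplicity adjustment.

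**The concern.** CRP is exploratory in Section 3, yet in Section 9 it is apparently one of three main hypotheses, tested like the primary. Suppose FIM is not significant and CRP or pain has p = 0.04. Under the Section 3 ranking the CRP result only generates a hypothesis. Under the Section 9 wording, either result could be written up as one of the study's main hypotheses met. The stated 0.05 applies to each test separately and does not cover the set. The position should be fixed before the data are seen, because a null primary is a realistic outcome in a trial expecting 30 completers.

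**Working it through.** **Inputs from the documents.** Three hypotheses (Section 1.1); two-sided 0.05 for each outcome and the same between-group test (Section 9.2.1); effect size 1.07 for FIM change, 30 completers, 80% power, 25% attrition and 40 enrolled (Section 9.1); 20:10 allocation (Sections 6.1.1 and 6.2).

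**Input assumed.** The correlation r between test statistics. The documents give none, so r = 0, 0.5 and 0.8 are shown.

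**1. The plan's own figures.** Power is taken from the noncentral t distribution with 28 degrees of freedom and noncentrality 1.07 × √(n1·n2/(n1+n2)).
- 15:15: 1.07 × √(225/30) = 2.93, power 80.7%. The stated 80% reproduces with equal groups.
- 20:10 as planned: 1.07 × √(200/30) = 2.76, power 76.0%.
- Enrolment: 30/(1 − 0.25) = 40, which reproduces.

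So even if the assumed FIM effect is true, a non-significant FIM result has a chance of about 100 − 76 = 24% at the planned allocation.

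**2. Which hypotheses does Section 9 mean?** It does not name pain or CRP. Section 1.1 lists exactly three hypotheses, so the natural reading is that these are the three. This is an inference, but a firm one.

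**3. Chance of at least one false positive, no true effect, one test per hypothesis.** For independent tests it is 1 − 0.95^k: k = 3 gives 1 − 0.8574 = 14.3%, and k = 2 gives 1 − 0.9025 = 9.75%. For equally correlated normal statistics it was found by numerical integration. The chance that the primary is non-significant while pain or CRP is significant is the three-test figure minus 5%.

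| r | All three | Pain and CRP only | Primary null, pain or CRP significant |
|---|---|---|---|
| 0 | 14.3% | 9.8% | 14.3 − 5 = 9.3% |
| 0.5 | 12.5% | 9.1% | 12.5 − 5 = 7.5% |
| 0.8 | 9.8% | 7.8% | 9.8 − 5 = 4.8% |

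These figures count errors in either direction, as two-sided tests do. Counting only errors favouring the exoskeleton, three independent tests give 1 − 0.975³ = 7.3%, against 2.5% for one test.

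**4. The primary is not one test.** Sections 1.1 and 3 list upper and lower motor scores, FIM and SCIM. With pain and CRP that makes six scores: 1 − 0.95⁶ = 26.5% if independent, and 20.7% at r = 0.5.

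**5. Does a gate restore 0.05?** Only if it rests on a single outcome. If any of three or four independent primary scores could open it, the first step alone has an error of 1 − 0.95³ = 14.3% or 1 − 0.95⁴ = 18.5%. With FIM alone as the gate and one fixed order after it, the chance of any false confirmatory claim is at most 5%, and FIM keeps its full 0.05. Bonferroni over three hypotheses (0.05/3 = 0.0167 each) would also protect the set, but would cut FIM power at 20:10 from 76.0% to 59.0%.

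**The case against.** The strongest reply is that the ranking exists and one loose adjective does not cancel it. Section 9.1 keeps FIM as the primary aim. Calling the three hypotheses main may be shorthand that separates them from the pre/post, dose and candidate analyses. Section 1.1 also words the CRP hypothesis more softly, without claiming significance. This is fair, and it rules out saying that Section 9 abandons the ranking altogether. It does not supply a rule: labels elsewhere do not tell the analyst what to conclude when FIM is null and pain is not.

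A reader might infer that a CRP or pain result at p = 0.04 becomes a confirmed finding under Section 9. The documents do not support that. Section 9 contains no rule for confirming a hypothesis and nothing on interpretation after a null primary. The gap is that nothing prevents such a presentation.

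A reader might also take Section 2.2 as a promise of equal-rank efficacy claims, since it speaks of an "efficacious approach to facilitate functional independence and to reduce post-SCI pain, as well as inflammation". In context, the authors expect the trial to determine whether this is so. That poses a question and needs no change.

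Finally, the three-test figures count a primary of three to four scores as one test, and they pool tiers that the sponsor ranks separately. Both points stand. The figures illustrate the scale of the problem and are not the error rate of this exact plan.

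**Conclusion.** The inconsistency is real and worth correcting. The analysis text tests pain and CRP on the same footing as the functional primary, while Section 3 calls CRP exploratory, and no rule governs what may be claimed after a null primary. With no true effect and one test per hypothesis, the chance of at least one false positive is 9.8% to 14.3%, about 2.0 to 2.9 times the stated 0.05. For pain and CRP alone it is 7.8% to 9.8%. These ranges rest on assumed equal correlations of 0.8 down to 0 and on reading the three main hypotheses as those in Section 1.1. Counting every primary score would raise the overall figure. The consequence is limited to what may be concluded; trial conduct is unaffected.

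**What to change.** In Sections 9.1 and 9.2.1, replace the reference to three main hypotheses with the Section 3 ranking and state:

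1. Change in FIM, already the primary aim and power basis in Section 9.1, is the single outcome tested first at two-sided 0.05.
2. The secondary hypothesis is tested on one named pain-intensity measure at two-sided 0.05, for a confirmatory claim only if FIM is significant. Otherwise it is reported as an estimate with a 95% confidence interval, labelled exploratory. The measure must be settled first: Section 1.1 uses a 7-day recall of worst pain, and Section 8.1 an average over three days.
3. CRP is reported as exploratory, with an estimate and 95% confidence interval and no confirmatory claim.
4. SCIM and the ISNCSCI motor scores are either placed after FIM in the sequence or reported as supportive. If they are in the sequence, their order relative to pain must be fixed, because testing several outcomes side by side at full 0.05 after FIM would lose the control.

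This needs no extra participants, data or procedures, and FIM power is unchanged. The price is that a significant pain result after a null FIM result, or any CRP result, can be presented only as hypothesis-generating.
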